2 INTRODUCTION

2.1 STUDY RATIONALE

Talimogene laherparepvec (T-VEC) is an herpes simplex virus type 1- (HSV-1-) based oncolytic virus designed to selectively replicate in tumors and produce granulocyte macrophage colony-stimulating factor (GM-CSF) to stimulate antitumor immune responses. T-VEC is administered by intratumoral injection and is currently under investigation as intralesional therapy for several solid tumor types. Intratumoral injection of T-VEC could result in an influx of infiltrating T cells mediated by direct tumor destruction, potentially initiating an immune response against tumor-associated antigens.

Cutaneous angiosarcoma (CA) is a difficult disease to treat, primarily due to the high recurrence rate and need for wide resection. CA is often associated with a prior history of radiation therapy and can respond well to taxane-based systemic therapy, which has been used effectively in the neoadjuvant setting. Unfortunately, recurrence is experienced by up to 75% of patients, including those treated with combination therapy, and they have no efficacious second-line treatment options available to them. The use of an intralesional immunomodulatory agent like T-VEC represents a novel approach for the treatment of patients whose disease is not controlled by standard therapy and have no other options. An early report of safety using T-VEC in advanced sarcoma patients was presented at ASCO 2018. Three CA patients were enrolled and 2 were classified as responders. The purpose of this trial is to validate this early response signal in a formal phase 2 trial for CA patients.

The goal of injecting T-VEC directly into the tumor is to stimulate both systemic and local anti-tumor responses. The insertion of a GM-CSF gene into the viral genome, as described in Section 2.2.2, will ideally create an adaptive immune response within the tumor, augmenting treatment and furthering the pathway to a complete response of the tumor and hopefully prevention of recurrence of cutaneous angiosarcoma.

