2.2 BACKGROUND

2.2.1 DISEASE BACKGROUND

CA is a rare cutaneous neoplasm that is classified as a soft tissue sarcoma which arises within the epidermis or dermis. The disease presents largely as 2 separate phenotypes. In one form, the cause is idiopathic and effects elderly men with a predilection for occurrence in the head and neck region. In another form, the disease is associated with a history of radiation therapy and most commonly affects women, with disease occurring in the skin of the breast after breast conservation therapy for primary breast cancer. The latter form occurs with a median latency period of 7 years between the exposure to radiation and development of a secondary malignancy.

Treatment for either condition is primarily wide surgical resection. Wide margins can be difficult to obtain as anatomic constraints often limit the resection. Even when primary resection is feasible, recurrence is common, with a local recurrence rate up to 60% for those with idiopathic cutaneous angiosarcoma and 75% for those with radiation-associated cutaneous angiosarcoma. Complicating treatment further is the presence of multifocal disease in both the primary and recurrent setting, which is difficult to manage with surgical resection. Despite the known association, radiation therapy has been advocated for cutaneous angiosarcoma as a way to increase local control.

With high local recurrence rates, there is an unmet need for local therapy. The anatomic constraints limiting resection in the primary setting are worse with recurrence and repeat radiation therapy to a site is generally not feasible. Systemic therapy is used for these patients; however, these options are often restricted by the limitations associated with the age of these often elderly patients.

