3 OBJECTIVES AND ENDPOINTS

Table 2: Objectives and Endpoints

OBJECTIVES	ENDPOINTS
Primary	
To evaluate the efficacy of T-VEC as treatment for relapsed/refractory cutaneous angiosarcoma	Overall response rate (ORR): the proportion of patients to demonstrate complete or partial responses in injected lesions per modified RECIST criteria appropriate for cutaneous neoplasms at 24 weeks.
Secondary	
1. To establish duration of response among treated patients	1. Response duration will be measured from the time of initial partial response or complete response until documented progression
2. To measure the rate of progression-free survival among treated patients	2. Progression-free survival: period from time of first injection to progression of disease or appearance of new CA tumors that were not present at the time of study entry
3. To measure the complete response (CR) rate for lesions that have complete clinical regression following study treatment	3. Complete Response rate: proportion of patients with pCR, defined as lesions with complete clinical regression
4. To monitor adverse events following administration of T-VEC injections	4. Incidence of adverse events from injection of T-VEC into cutaneous angiosarcoma
5. To measure the rate of patients requiring surgical resection of T-VEC–treated lesions	5. Proportion of patients whose T-VEC–treated tumors require surgical resection
6. To measure the degree of immune infiltration in surgically resected T-VEC–treated tumors	6. Immunohistochemistry and flow cytometry analyses of immune infiltration within resected tumor specimens
Tertiary/Exploratory	
1. To measure the degree of immune infiltration in surgically resected T-VEC–treated tumors	1. Immunohistochemistry and flow cytometry analyses of immune infiltration within resected tumor specimens to determine patterns of lymphocyte infiltration associated with response
2. To evaluate surgical outcomes for those patients whose T-VEC–treated tumors are resected	Surgical outcomes recorded will include margin status, percent viable tumor, postoperative complications, and disease-free interval following resection.

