5 STUDY POPULATION

5.1 INCLUSION CRITERIA

To be eligible to participate in this study, an individual must meet all of the following criteria:

1. Provision of signed and dated informed consent form
2. Stated willingness to comply with all study procedures and availability for the duration of the study
3. Adult male or female, aged 18 years and over
4. Patients must have histologically confirmed CA without visceral or CNS metastases, with resection deemed of no benefit by technical or oncologic principles, and have progressed on at least one line of systemic therapy
5. Patients must have measurable disease, defined as at least one lesion that can be accurately measured in at least one dimension (longest diameter to be recorded by digital photography) as ≥ 6 mm with calipers or a ruler.
6. Eastern Cooperative Oncology Group performance status 0-1 (Karnofsky $\geq 70\%$).
7. Patients must have normal organ and marrow function as defined below:
 - a. Hematological
 - i. - Absolute neutrophil count $\geq 1500/\text{mm}^3$ ($1.5 \times 10^9/\text{L}$)
 - ii. - Platelet count $\geq 75,000/\text{mm}^3$ ($7.5 \times 10^9/\text{L}$)
 - iii. - Hemoglobin $\geq 8 \text{ g/dL}$ (without need for hematopoietic growth factor or transfusion support)
 - b. Renal
 - i. - Serum creatinine $\leq 1.5 \times$ upper limit of normal (ULN), OR 24-hour creatinine clearance $\geq 60 \text{ mL/min}$ for subject with creatinine levels $> 1.5 \times$ ULN. (Note: Creatinine clearance need not be determined if the baseline serum creatinine is $\leq 1.5 \times$ ULN. . Creatinine clearance should be determined per institutional standard).
 - c. Hepatic
 - i. - Serum bilirubin $\leq 1.5 \times$ ULN OR direct bilirubin \leq ULN for a subject with total bilirubin level $> 1.5 \times$ ULN
 - ii. - Aspartate aminotransferase (AST) $\leq 2.5 \times$ ULN OR $< 5 \times$ ULN, if liver metastases present and injection does not involve a visceral lesion
 - iii. - Alanine aminotransferase (ALT) $\leq 2.5 \times$ ULN OR $< 5 \times$ ULN, if liver metastases present and injection does not involve a visceral lesion
 - d. Coagulation
 - i. - International normalization ratio (INR) or prothrombin time (PT) $\leq 1.5 \times$ ULN, unless the subject is receiving anticoagulant therapy, in which case PT and partial thromboplastin time (PTT)/ activated PTT (aPTT) must be within therapeutic range of intended use of anticoagulants.

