5.2 EXCLUSION CRITERIA

An individual who meets any of the following criteria will be excluded from participation in this study:

1. Patients with a second active malignancy, exceptions are localized non-melanoma skin cancers or in situ carcinoma
2. Patients receiving any other investigational agents
3. Participants with tumor(s) in direct contact or encasing a major blood vessel, those with ulceration and/or fungation onto the skin surface, and those with history of re-irradiation or prior lymph node neck dissection to a field involving the carotid arteries
4. History or evidence of active autoimmune disease that requires systemic treatment (ie, with use of disease modifying agents, corticosteroids or immunosuppressive drugs). Replacement therapy (eg, thyroxine, insulin, or physiologic corticosteroid replacement therapy for adrenal or pituitary insufficiency, etc.) is not considered a form of systemic treatment.
5. Evidence of clinically significant immunosuppression such as the following:
 - a. - Primary immunodeficiency state such as Severe Combined Immunodeficiency Disease.
 - b. - concurrent opportunistic infection.
 - c. - receiving systemic immunosuppressive therapy (> 2 weeks) including oral steroid doses > 10 mg/day of prednisone or equivalent within 7 days prior to enrollment.
6. Active herpetic skin lesions or prior complications of HSV-1 infection (e.g., herpetic keratitis or encephalitis).
7. Requires intermittent or chronic systemic (intravenous or oral) treatment with an antiherpetic drug (e.g., acyclovir), other than intermittent topical use.
8. Previous treatment with talimogene laherparepvec or any other oncolytic virus.
9. Prior therapy with tumor vaccine.
10. Received live vaccine within 28 days prior to enrollment.
11. Prior immunosuppressive, chemotherapy, radiotherapy (in which the field encompassed a planned injection site), biological cancer therapy, or major surgery within 28 days prior to enrollment or has not recovered to CTCAE grade 1 or better from adverse event due to cancer therapy administered more than 28 days prior to enrollment.
12. Prior radiotherapy in which the field does not overlap the injection sites or non-immunosuppressive targeted therapy within 14 days prior to enrollment or has not recovered to CTCAE grade 1 or better from adverse event due to cancer therapy administered more than 14 days prior to enrollment

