8.1.2.1 DEFINITIONS

Evaluable for toxicity. All patients will be evaluable for toxicity from the time of their first treatment with T-VEC

Evaluable for objective response. Only those patients who have measurable disease present at baseline, have received at least three injections at the 10^8 dose level, and have had their disease re-evaluated will be considered evaluable for response. These patients will have their response classified according to the definitions stated below.

Evaluable Non-Target Disease Response. Patients who have lesions present at baseline that are evaluable but do not meet the definitions of measurable disease, have received at least one cycle of therapy, and have had their disease re-evaluated will be considered evaluable for non-target disease. The response assessment is based on the presence, absence, or unequivocal progression of the lesions.

Disease Parameters

Measurable disease. Measurable lesions are defined as those that can be accurately measured in at least one dimension (longest diameter to be recorded) as ≥ 6 mm by calipers on clinical examination. All tumor measurements must be recorded in millimeters (or decimal fractions of centimeters).

Non-measurable disease. All other lesions (or sites of disease), including small lesions (longest diameter < 6 mm) are considered non-measurable disease.

Note: Cystic lesions that meet the criteria for radiographically defined simple cysts should not be considered as malignant lesions (neither measurable nor non-measurable) since they are, by definition, simple cysts.

“Cystic lesions” thought to represent cystic metastases can be considered as measurable lesions if they meet the definition of measurability described above. However, if non-cystic lesions are present in the same patient, these are preferred for selection as target lesions.

Target lesions. All measurable lesions up to a maximum of 5 lesions in total, representative of all involved organs, should be identified as **target lesions** and recorded and measured at baseline. Target lesions should be selected on the basis of their size (lesions with the longest diameter), but in addition should be those that lend themselves to

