8.1.2.3 RESPONSE CRITERIA

Evaluation of Target Lesions

Complete Response (CR): Disappearance of all target lesions.

Partial Response (PR): At least a 30% decrease in the sum of the diameters of target lesions, taking as reference the baseline sum diameters.

Progressive Disease (PD): At least a 20% increase in the sum of the diameters of target lesions, taking as reference the smallest sum on study (this includes the baseline sum if that is the smallest on study). (Note: the appearance of one or more new lesions is also considered progression).

Stable Disease (SD): Neither sufficient shrinkage to qualify for PR nor sufficient increase to qualify for PD, taking as reference the smallest sum diameters while on study.

Evaluation of Non-Target Lesions

Complete Response (CR): Disappearance of all non-target lesions and normalization of tumor marker level.

Progressive Disease (PD): Appearance of one or more new lesions and/or unequivocal progression of existing non-target lesions. Unequivocal progression should not normally trump target lesion status. It must be representative of overall disease status change, not a single lesion increase.

Although a clear progression of “non-target” lesions only is exceptional, the opinion of the treating physician should prevail in such circumstances, and the progression status should be confirmed at a later time by the review panel (or Principal Investigator). Photography of these changes is recommended.

Evaluation of Best Overall Response

The best overall response is the best response recorded from the start of the treatment until disease progression/recurrence (taking as reference for progressive disease the smallest measurements recorded since the treatment started). The patient's best response assignment will depend on the achievement of both measurement and confirmation criteria.

Overall Response Criteria

Target Lesions	Non-Target Lesions	New Lesions	Overall Response	Best Overall Response when Confirmation is Required
CR	CR	No	CR	≥ 4 wk Confirmation
CR	Non-CR/Non-PD	No	PR	≥ 4 wk Confirmation
CR	Not evaluated	No	PR	
PR	Non-CR/Non-PD/not evaluated	No	PR	
SD	Non-CR/Non-PD/not evaluated	No	SD	Documented at least once ≥ 4 wk from baseline
PD	Any	Yes or No	PD	No prior SD, PR, or CR
Any	PD***	Yes or No	PD	
Any	Any	Yes	PD	

*** In exceptional circumstances, unequivocal progression in non-target lesions may be accepted as disease progression.

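### No entry criterion requires progression or recurrence since the last treatment, so shrinkage carried over from pre-study therapy can be scored as a T-VEC response

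*Combined protocol and SAP*

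**What the plan says.** - **Entry.** Section 5.1, item 4 requires that patients "have progressed on at least one line of systemic therapy". It does not say which line, or that the disease has grown since the last treatment. Item 5 sets a size threshold (6 mm) and nothing about recent growth.
- **Washout.** Section 5.2, item 11 covers chemotherapy and "radiotherapy (in which the field encompassed a planned injection site), biological cancer therapy, or major surgery within 28 days prior to enrollment". Item 12 covers "Prior radiotherapy in which the field does not overlap the injection sites or non-immunosuppressive targeted therapy within 14 days prior to enrollment". Both pair the day count with recovery from adverse events, not with evidence of progression.
- **Target lesions.** Section 8.1.2.1: "All measurable lesions up to a maximum of 5 lesions in total, representative of all involved organs, should be identified as" target lesions. Selection is by size and reproducibility of measurement, and every target lesion is injected. Lesions in an old radiation field, or lesions already regressing, are not mentioned.
- **Response.** Section 8.1.2.3 defines partial response as "At least a 30% decrease in the sum of the diameters of target lesions, taking as reference the baseline sum diameters".
- **Intended population.** Section 3, Table 2 gives the primary objective: "To evaluate the efficacy of T-VEC as treatment for relapsed/refractory cutaneous angiosarcoma".
- **Decision rule.** Section 9.2: stop if 1 or fewer of 8 respond; otherwise treat 13 in total and reject the treatment if 3 or fewer respond. Stated error rates are 0.031 and 0.198, against targets of 0.050 and 0.200.

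**The concern.** Take a patient who progressed on one drug some time ago and was then irradiated over the lesion, or treated with a second drug, with that treatment ending 29 days before enrollment. If the lesion is still shrinking, the prior-therapy criteria are met and the lesion can be chosen as a target and injected. Further shrinkage of 30% would count toward the primary endpoint.

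The protocol's own background makes such carry-over conceivable. Section 2.2.1 notes that "radiation therapy has been advocated for cutaneous angiosarcoma as a way to increase local control", and Section 2.1 says the disease "can respond well to taxane-based systemic therapy, which has been used effectively in the neoadjuvant setting".

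The trial has one arm, so nothing inside it separates carry-over from drug effect. The only comparator is the fixed 10% null rate, and that rate is a fair reference only if responses come from T-VEC. Any carry-over pushes the response rate upward, and with a threshold of 4 in 13 a single patient matters.

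**Working it through.** **Inputs.** From Sections 9.1 and 9.2: P0 = 0.10, P1 = 0.40, n1 = 8 (continue with 2 or more responses), n = 13 (success with 4 or more). The number or rate of carry-over responders is an assumption; the documents give none.

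**Step 1: reproduce the plan.** With X1 ~ Bin(8, p) and X2 ~ Bin(5, p):

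P(success) = P(X1=2)·P(X2≥2) + P(X1=3)·P(X2≥1) + P(X1≥4)

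At p = 0.10: 0.1488 × 0.0815 + 0.0331 × 0.4095 + 0.0050 = 0.0307. The probability of early termination is 0.4305 + 0.3826 = 0.8131, and the expected sample size is 8 + 5 × 0.1869 = 8.93. At p = 0.40 the power is 0.8015. These agree with Section 9.2.

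**Step 2: fixed number of carry-over responders.** Each is counted as a certain responder; all other patients respond with probability 0.10.

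- *One in stage 1* (7 others in stage 1, 5 in stage 2): 0.3720 × 0.0815 + 0.1240 × 0.4095 + 0.0257 = **0.107**. The chance of passing stage 1 becomes 1 − 0.9^7 = 0.522, against 0.187 without carry-over.
- *One in stage 2* (8 in stage 1, 4 others in stage 2): 0.1488 × 0.3439 + 0.0381 = **0.089**.
- *Two in stage 2*: any trial passing stage 1 already reaches 4, so the probability is 1 − 0.8131 = **0.187**.
- *One in each stage*: 0.3720 × 0.3439 + 0.1497 = **0.278**.
- *Two in stage 1* (6 others in stage 1): 0.5314 × 0.0815 + 0.3543 × 0.4095 + 0.1143 = **0.303**.

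**Step 3: carry-over as a rate.** If a share c of patients would be scored as responders from prior therapy alone, the effective null rate is 0.10 + 0.90c. The Step 1 formula then gives:

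| c (assumed) | Effective null rate | P(success) |
|---|---|---|
| 0 | 0.100 | 0.031 |
| 2% | 0.118 | 0.052 |
| 5% | 0.145 | 0.097 |
| 10% | 0.190 | 0.204 |

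The plan's 0.05 target is passed at c of about 1.8%.

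**Step 4: would another rule catch it?** Confirmation at 4 weeks or more (Section 8.1.2.3) and the requirement of three injections at the higher concentration (Section 8.1.2.1) filter out short-lived changes and early dropouts, but do not identify the cause of shrinkage. Photography (Section 6.3) documents size. In the Schedule of Activities, tumor measurement starts at week −1, so no pre-entry growth trend is recorded.

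**The case against.** The strongest reply is that the documents describe a population in which this should be rare. Section 2.1 says recurrent patients have no efficacious second-line option, which weakens the route through a working second drug. Section 2.2.1 says repeat radiotherapy to a site is generally not feasible, which weakens the radiotherapy route, though first-time irradiation of a site remains possible. The title and objectives speak of recurrent or relapsed/refractory disease, and enrolling a patient whose disease is still regressing would go against that intent. A carry-over response would also have to survive the washout, reach a further 30% fall in the sum of up to five lesions with no new lesion, and be confirmed.

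Much of this stands: it narrows the path and argues for low frequency. It does not close the path, because no eligibility criterion puts the stated intent into effect.

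A reader might infer three stronger things that the documents do not support:

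- *That a regressing lesion has to be a target.* Section 8.1.2.1 says lesions should be selected, caps them at five, and lets a lesion that cannot be measured reproducibly be passed over. Such a lesion can be a target; it need not be.
- *That the 14-day washout for radiotherapy away from the injection sites is a further route.* It is not, because all target lesions are injected.
- *That the trial's type I error is 0.107 rather than 0.031.* The higher figures apply only if a carry-over responder is enrolled.

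**Conclusion.** The gap in the text is real. As written, the rules allow shrinkage from pre-study treatment to be credited to T-VEC, and the bias can only run upward. Its frequency is unknown and may well be low. Its consequence if it occurs is large for a trial of 13: one carry-over responder roughly triples the false-positive probability (0.031 to 0.089 or 0.107), and two bring it to between 0.19 and 0.30. These results assume a true T-VEC response rate of 10% and carry-over patients who are certain to be scored as responders. The plan's stated design figures are correct and are not in dispute. This is an inexpensive clarification worth making, not evidence that the design fails.

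**What to change.** 1. **Section 5.1, item 4:** align it with the relapsed/refractory objective by requiring documented progression or recurrence since the most recent anticancer therapy.
2. **Section 8.1.2.1:** state that a lesion in a previously irradiated field may be a target lesion only if it appeared or grew after that radiotherapy.
3. **Reporting:** beside each responder, list the last prior therapy, its end date, and any radiotherapy to the target lesions.

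Separately, as a drafting matter, reconcile the radiotherapy-field wording of exclusions 11 and 12. One speaks of a field that encompasses an injection site and the other of a field that does not overlap it, so a partly overlapping field falls under neither.

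**Cost.** Wording in Sections 5.1, 5.2 and 8.1.2.1, and a case report form field; medical history is already collected. Item 1 means that patients still regressing, or with stable residual disease after stopping a later therapy, would wait or not be enrolled. At the expected one patient per month (Section 5.5), that may slow accrual slightly. Items 2 and 3 alone avoid most of that cost, but leave the drug route open to carry-over and only make it visible in the report. Sample size, cut-offs and design error rates are unchanged.

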1.2 SCHEMA

1.3 SCHEDULE OF ACTIVITIES (SOA)

For explanation of procedures, please see Section 8 (Study Assessments and Procedures).

Baseline evaluations are to be conducted within 1 week prior to start of protocol therapy. Imaging must be done within 4 weeks prior to the start of therapy and then every three months starting at week 12. In the event that the patient's condition is deteriorating, laboratory evaluations should be repeated within 48 hours prior to initiation of the next cycle of therapy.

Table 1: Schedule of Activities

	Wk -4	Wk -1	Wk 1	Wk 2	Wk 3	Wk 4 and Bi-weekly	Wk 12 and every three months	Off Study ^e
T-VEC ^a			X			X	X	
Informed consent		X						
Demographics		X						
Medical history		X						
Concurrent meds		X	X	X	X	X	X	X
Physical exam		X	X			X	X	X
Imaging	X						X	
Vital signs		X	X	X	X	X	X	X
Height		X						
Weight		X	X	X	X	X	X	X
Performance status		X	X			X	X	X
Complete blood panel w/diff, platelets		X	X			X	X	X
CMP ^b		X	X			X	X	X
EKG		X						
Coagulation studies (PT/PTT/INR)		X						
Adverse event evaluation		X	X	X	X	X	X	X
Tumor measurements – ruler/calipers and digital photography of lesions		X	X	X	X	X	X	X
Punch biopsy ^c		X						X
B-HCG blood pregnancy test		X ^d						

a. Talimogene laherparepvec (T-VEC): Dose as assigned; *administration schedule only applies if tumor is visualized*. Dose 2 to be given 21 days after dose 1 with window of +3 days. Window for remaining doses is +/- 3 days.

b. Comprehensive Metabolic Panel: Albumin, alkaline phosphatase, total bilirubin, bicarbonate, BUN, calcium, chloride, creatinine, glucose, , potassium, total protein, SGOT [AST], SGPT [ALT], sodium.

c. Punch biopsy will be performed using a 4-6 mm punch, up to 2 biopsies per instance.

d. Serum pregnancy test (women of childbearing potential) completed within 72 hours of enrollment.

e. Patients will be treated for a maximum of 52 weeks per section 6.1.2.3. Off-study treatment evaluation should be completed within 30 days after last T-VEC treatment. Patients will continue to be followed-up posttreatment to determine RFS and note any complications; patients will also be followed every 6 months (+/- 1 month) for 2 years by telephone, review of follow-up notes for recurrence status and latent herpetic infection.

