4 STUDY DESIGN

4.1 OVERALL DESIGN

This is a single-center, single-arm, phase 2 study to evaluate the efficacy of intratumoral injection with talimogene laherparepvec (T-VEC) as monotherapy in relapsed/refractory locally advanced cutaneous angiosarcoma (CA) tumors. The hypothesis is that intralesional therapy using T-VEC will result in an objective response (CR or PR) in these patients. There will be no dose modifications from the current FDA-approved dose for other indications. Specific details regarding dosing and administration can be found in section 6.1.2. There are no stratifications in this trial.

Patient enrollment will follow a Simon's 2-stage design, assuming that at least a P0 response rate of 10% will be reached for injected lesions. In the first stage, 8 patients will be accrued. If there is > 1 response in these 8 patients, the study will enroll 5 additional patients for a total of 13. The null hypothesis will be rejected if 4 or more responses are observed in 13 patients. This design yields a type I error rate of 0.03 and power of 0.8 when the P1 response rate is 40%.

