8 STUDY ASSESSMENTS AND PROCEDURES

8.1 EFFICACY ASSESSMENTS

8.1.1 PRE-STUDY PROCEDURES

To be performed no more 4 weeks prior to initiation of study treatment

Imaging: CT chest, abdomen, and pelvis with IV contrast

To be performed within 1 week of 1st study treatment evaluation

Informed consent, demographics, concomitant medications, performance status, physical examination, vitals, height, weight, complete blood count, complete metabolic panel, serum pregnancy test completed within 72 hours of enrollment, serum HSV1 Ab, electrocardiogram, tumor measurement by palpation/exam, request slides from tumor biopsies for immunohistochemical analysis.

Week 1 procedures:

Complete blood count, complete metabolic panel, pharmacy to begin thawing/preparation of dose, clinic visit with concurrent medications, performance status, physical examination, vitals, weight, tumor measurement by examination, injection of T-VEC into primary tumor.

Weeks 2, 3 and 6:

Clinic visit with concurrent medications, performance status, physical examination, vitals, weight, anti-HSV Ab titer on week 6 only

Bi-weekly procedures starting Week 4-week 52:

Complete blood count, complete metabolic panel, pharmacy to begin thawing/preparation of dose, clinic visit with concurrent medications, performance status, physical examination, vitals, weight, tumor measurement by examination, injection of T-VEC into primary tumor.

Off-study procedures:

Complete blood count, complete metabolic panel, clinic visit with concurrent medications, performance status, physical examination, vitals, weight, and punch biopsy all within 30 days of last study treatment. Follow up of any treatment-related adverse events until resolution, stabilization, or death for a minimum of 30 days after last study treatment. Data on any perioperative complications should be also collected as applicable. Final tumor

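### The platelet eligibility limit of 75,000/mm³ is wrongly converted in its bracket to 7.5 × 10⁹/L; the correct figure is 75 × 10⁹/L

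*Combined protocol and SAP*

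**What the plan says.** Section 5.1 (Inclusion Criteria) lists conditions that every participant must meet. Item 7 opens with "Patients must have normal organ and marrow function as defined below" and then gives the laboratory limits.

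- Item 7.a.i, neutrophils: "Absolute neutrophil count $\geq 1500/\text{mm}^3$ ($1.5 \times 10^9/\text{L".
- Item 7.a.ii, platelets: "Platelet count $\geq 75,000/\text{mm}^3$ ($7.5 \times 10^9/\text{L".

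Each line gives a count per mm³ followed by a bracketed SI equivalent. The Schedule of Activities (Section 1.3) includes platelets in the blood count but attaches no limit to them. The dose-delay and discontinuation rules in Section 6.1.2.3 act on treatment-related toxicity after entry and give no platelet number. The limit in item 7.a.ii is therefore the only numeric platelet threshold in the document.

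**The concern.** The bracket should restate the same limit in other units. Instead it gives a different one, so a single mandatory criterion carries two thresholds a factor of ten apart. A patient at 50 × 10⁹/L (50,000/mm³), for example, fails the leading figure and passes the bracketed one.

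The practical route to error is someone who works in SI units, or who copies the bracket into an eligibility checklist or a database range check. Platelet count bears on bleeding risk, and the protocol is procedural: "Punch biopsy will be performed using a 4-6 mm punch, up to 2 biopsies per instance", plus intralesional injections through the treatment year. Items 7.d.i and 7.d.ii also allow patients on anticoagulants to enter. The issue is eligibility and safety, not inference.

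**Working it through.** **Inputs**, all from Section 5.1, item 7.a:

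- Neutrophil limit: 1,500/mm³, bracket 1.5 × 10⁹/L.
- Platelet limit: 75,000/mm³, bracket 7.5 × 10⁹/L.

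**Formula.** 1 L = 10⁶ mm³, so count per litre = count per mm³ × 10⁶.

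**Control line (neutrophils).** 1,500 × 10⁶ = 1.5 × 10⁹/L. The printed bracket is reproduced exactly (ratio 1.0), which confirms the convention the list uses.

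**Platelets.** 75,000 × 10⁶ = 7.5 × 10¹⁰/L = 75 × 10⁹/L. The printed 7.5 × 10⁹/L is not reproduced.

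**The bracket in the other direction.** 7.5 × 10⁹ ÷ 10⁶ = 7,500/mm³.

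| Line | Per mm³ | Correct SI value | Printed SI value | Correct ÷ printed |
|---|---|---|---|---|
| Neutrophils | 1,500 | 1.5 × 10⁹/L | 1.5 × 10⁹/L | 1 |
| Platelets | 75,000 | 75 × 10⁹/L | 7.5 × 10⁹/L | 10 |

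**Which figure is meant.** The leading figure is 75,000/mm³, and the stem of item 7 asks for normal marrow function. A limit of 7,500/mm³ cannot fit that stem, so the slip is in the bracket: a misplaced decimal point, or an exponent of 9 where 10 was needed.

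**Range affected, only on a literal reading of the bracket.** 7.5 to just under 75 × 10⁹/L.

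**Procedures a participant could undergo.** These show why a platelet limit matters here; they do not measure the effect of the error.

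- Injection visits: one at week 1, then "Bi-weekly procedures starting Week 4-week 52" in Section 8.1.1, which gives (52 − 4)/2 + 1 = 25 more. The maximum is 26.
- Punch biopsies: the Schedule of Activities marks two time points (week −1 and off study) with up to 2 biopsies each, so up to 4. Section 8.1.1 lists a punch biopsy only among the off-study procedures and asks before treatment for slides from tumor biopsies. On that section alone the maximum would be 2.

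**Effect on the statistics.** None. The two-stage design in Section 9.2 depends on the response rates (0.10 and 0.40), the stage sizes (8 and 13) and the cut-offs. The platelet limit enters none of these.

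**The case against.** The arithmetic is not in dispute. The case on the other side concerns its consequence and its source.

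1. **The operative limit is clear.** The criterion leads with 75,000/mm³ and the bracket is a gloss. Misapplying it means passing over the leading figure and accepting 7,500/mm³ as normal marrow function. Section 4.1 says "This is a single-center, single-arm, phase 2 study", so there are no other sites to read the line differently. This stands, and it keeps the likelihood low.

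2. **There is a partial backstop.** Exclusions 11 and 12 in Section 5.2 bar patients whose adverse events from earlier cancer therapy have not recovered to CTCAE grade 1. Everyone enrolled has progressed on systemic therapy, so this covers an important cause of low platelets and narrows the group who could enter even on a literal reading. It states no platelet number and does not reach other causes, so it does not repair the criterion.

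3. **The slip may lie in the text conversion.** If the source page has 75 in place of 7.5, or 10¹⁰ in place of 10⁹, the plan contains no error. This cannot be fully excluded. Against it, the line is complete and well formed, and the neutrophil line with the same layout reads correctly. A check against the source page settles it.

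4. **Visit and biopsy counts do not measure the error.** Agreed. They are context only, and no bleeding risk is derived from them.

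**Conclusion.** The criterion is wrong as written: its bracketed SI value is too low by a factor of 10. The conversion is a fixed unit identity and needs no outside figure. Two assumptions remain: that the line is printed in the source as it reads here, and that 75,000/mm³ is the intended limit, which its leading position and the item stem both support.

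The point is minor. Wrongful enrollment would require a literal reading of the bracket at a single center where the right figure comes first, and design, error rates and endpoints are unaffected. It still deserves correction, because it is the only platelet threshold in the protocol and it governs entry.

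**What to change.** Check the bracket against the source page. If it is printed as it reads here, change it at the next amendment so that item 7.a.ii gives a platelet count of at least 75,000/mm³ (75 × 10⁹/L). Make sure any eligibility checklist or database range check built from this line uses the same value.

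The cost is one figure. Nothing in the design, sample size or analysis changes.
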